3.5.1.1. AE SEVERITY

The severity of AEs will be rated on a 3-point scale:

- Mild: discomfort noticed but no disruption of normal daily activity
- Moderate: discomfort sufficient to reduce or affect normal daily activity
- Severe: incapacitating with inability to work or perform normal daily activity

It is emphasized that the term severe is a measure of intensity: a severe AE is not necessarily serious. For example, itching for several days may be rated as severe, but may not be clinically serious.

Please refer to the Common Terminology Criteria for Adverse Events (CTCAE v4.0) as guidance for assessment of severity of laboratory abnormalities if considered clinically significant by the Investigator.

3.5.1.2. OUTCOME

The outcome of the AE is to be documented as follows:

- Recovered/resolved
- Recovering/resolving
- Recovered/resolved with sequelae
- Not recovered/not resolved
- Fatal
- Unknown

3.5.1.3. RELATION TO DRUG OR STUDY PROCEDURES

The assessment of the causal relationship between an AE and the administration of treatment is a clinical decision based on all available information.

The assessment is based on the question whether there was a “reasonable causal relationship” to the study treatment in question. Possible answers are:

- Unlikely/Not related
- Possibly related
- Related
- Not applicable

Assessment of causal relationship of any AE to PE or use of corticosteroids can be completed with:

- Yes
- No
- Not applicable

3.5.1.4. ACTION TAKEN REGARDING STUDY DRUG

Any action taken regarding the study drug is to be documented using following categories:

- Dose not changed
- Drug interrupted
- Drug withdrawn
- Not applicable
- Unknown

3.5.2. SERIOUS ADVERSE EVENTS

An SAE is any untoward medical occurrence that meets any of the following conditions:

- Results in death.
- Is life-threatening: the subject is at risk of death at the time of the event. It does not refer to an event that hypothetically might cause death if it were more severe.
- Requires in-patient hospitalization or prolongation of existing hospitalization; an AE associated with a hospitalization or prolongation of hospitalization will not be regarded as an SAE if at least one of the following exceptions is met:
 - The admission results in a hospital stay of less than 12 hours.
 - The admission is pre-planned (i.e., elective or scheduled surgery arranged prior to the start of the study).
 - The admission is not associated with an AE (e.g., social hospitalization for purposes of respite care).

However, it should be noted that invasive treatment during any hospitalization may fulfill the criterion of "medically important" and as such may be reportable as an SAE dependent on clinical judgment. In addition, where local regulatory authorities specifically require a more stringent definition, the local regulation takes precedence.

- Results in persistent or significant disability/incapacity. Disability means a substantial disruption of a person's ability to conduct normal life's functions.
- Results in a congenital anomaly/birth defect.
- Is another medically important serious event as judged by the Investigator, or is defined as requiring intervention to prevent one of the outcomes listed in the definition above (including suspected transmission of an infectious agent by a medicinal product should be reported as an SAE). Other examples of such events are intensive treatment in an emergency room or at home for allergic bronchospasm; blood dyscrasias or convulsions that do not result in hospitalization; or development of drug dependency or drug abuse. Any AE is considered an SAE if it is associated with clinical signs or symptoms judged by the Investigator to have a significant clinical impact.

All exacerbations and relapses must be considered covered by the "another medically important serious event" criterion and must be reported as SAE.

The Investigator or clinical site personnel should notify the contract research organization (CRO) of all SAEs, regardless of relationship to the study drug, within 24 hours of clinical site personnel becoming aware of the event (see Investigator Site File).

The Investigator will provide the initial notification by faxing a completed "SAE Notification Form", which must include the Investigator's assessment of the relationship of the event to study drug, and must be signed by the Investigator.

The first report of an SAE may also be made by telephone. The Reporter must provide the minimal information: i.e., reporter identification, study number, year of birth, on medication (yes/no), period of intake, nature of the AE, and relation to study drug (if applicable).

This report of an SAE by telephone must always be confirmed by a written, more detailed report (the SAE Form) to be completed and signed by the Investigator.

Follow-up information, or new information regarding an ongoing SAE, must be provided promptly to the contacts provided in the Investigator Site File.

The SAE should also be recorded in the eCRF. Any medications necessary for the treatment of the SAE must be recorded on the concomitant medication section of the eCRF.

SAEs that begin after the subject's participation in the study is complete, but that the Investigator considers to be related to study drug, should be reported to the CRO/Sponsor at any time.

3.5.3. SUSPECTED UNEXPECTED SERIOUS ADVERSE REACTIONS

Unexpected adverse reactions are adverse reactions of which the nature or severity is not consistent with the applicable product information (as described in the Reference Safety Information, provided in the Investigator's Brochure).

The CRO will expedite reports of the following SUSARs to the IEC/IRB on behalf of the Sponsor:

- SUSARs that have arisen in the current clinical study that was assessed by the IEC/IRB.
- SUSARs that have arisen in other clinical studies of the same Sponsor and with the same study drug and that could have consequences for the safety of the subjects involved in the current clinical study that was assessed by the IEC/IRB.

The CRO will expedite all reports of SUSARs to the relevant CA on behalf of the Sponsor.

The Sponsor (or the CRO on behalf of the Sponsor) will also report to all concerned Investigators all SAEs that are unlisted (unexpected) and associated with the use of the drug.

The expedited reporting will occur no later than 15 calendar days after the Sponsor (or the CRO on behalf of the Sponsor) has first knowledge of the adverse reactions.

For fatal or life-threatening cases the term will be maximal 7 calendar days for a preliminary report with another 8 days for completion of the report.

3.5.4. REPORTING OF ADVERSE EVENTS

AEs reporting, including SUSARs, will be carried out in accordance with applicable local regulations. For reported deaths, the Investigator should supply the Sponsor and the IEC/IRB with any additional requested information (e.g., autopsy reports and terminal medical reports).

After termination of the clinical study (last subject last visit in the study), any unexpected safety issue that changes the risk benefit analysis and is likely to have an impact on the subjects who have participated in it, will be reported by the Sponsor as soon as possible to the competent authority(ies) concerned together with proposed actions.

3.5.5. FOLLOW-UP OF ADVERSE EVENTS

AEs will be handled according to common clinical practice. If necessary, in order to obtain additional information to ensure safety to the subject, additional blood and urine samples may be taken at the discretion of the Investigator. Information relative to other means of investigational diagnostics used in relation to the AE will also be communicated.

All AEs occurring during the study will be followed until stable outcome.

3.5.6. OTHER REPORTABLE INFORMATION

3.5.6.1. PREGNANCY

The Investigator must report to the Sponsor any pregnancy occurring in a subject receiving treatment with caplacizumab, or in his partner, during treatment with caplacizumab and within 2 months after the last dose of caplacizumab.

All pregnancy will be documented on the Pregnancy Report provided to the Investigator. The report should be submitted within the same timelines as an SAE, although a pregnancy per se is not considered an SAE. The progression of the pregnancy and the eventual birth (if applicable) must be followed-up using the Pregnancy Report in which the Investigator has to report on the health of the mother and of the child. The health of the child must be followed for 30 days after birth for any significant medical issues.

A pregnancy becomes an SAE in the following circumstances: miscarriage, abortion, or anomaly/birth defect of the child. Those SAEs must be additionally reported using the Investigator SAE Report form.

Note that as indicated in section 3.2.4, subjects who get pregnant during treatment with caplacizumab should be withdrawn from study treatment (not from the study).

3.5.6.2. MEDICATION ERROR

Medication errors include, but are not limited to, the following:

- Administration of the wrong dosage (including overdose) to the subject.
- Administration of the study drug that has not been assigned to the subject.
- Administration to a subject that does not have a TTP recurrence episode.
- Administration of expired study drug.
- Administration by a route (e.g., intramuscularly) other than i.v. or s.c.
- Deviations to the study drug storage conditions only when administered to the subject.

Medication errors with signs and symptoms need to be reported as an AE/SAE.

Medication errors that occur during the study should be documented and reported to the Sponsor or designee whether or not it results in an AE/SAE.

3.6. STATISTICS

3.6.1. STUDY POPULATIONS

The following populations will be considered for analysis:

- **Intention-to-observe (ITO) population:** All subjects who enrolled in Study ALX0681-C302.
- **Recurrence population:** All subjects in the ITO population who have experienced at least one recurrence in Study ALX0681-C302.

Unless otherwise specified, the ITO population will be used for the analysis of the Q6M FU data on efficacy, disease-related markers, PD, immunogenicity and safety. The recurrence population will be used for analysis of data collected during recurrence periods. Depending on whether subjects have been treated with caplacizumab or not, or have been retreated with caplacizumab, different subsets of the recurrence population may be defined for specific analyses. This will be detailed in the statistical analysis plan (SAP).

3.6.2. STATISTICAL AND ANALYTICAL PLAN

Interim analyses may be conducted in view of supporting regulatory submissions.

All data for enrolled subjects will be loaded in the database, and will be cleaned prior to final database lock (or interim database lock, if applicable) according to the specifications detailed in a data validation plan.

The SAP will be generated under responsibility of the Sponsor and will be finalized prior to final database lock (or interim database lock in case of an interim database lock). Any deviation from the reporting and analysis plans will be reported in the section "Changes in the planned analysis" in the Clinical Study Report. Details of the data analyses will be specified in the SAP.

3.6.3. DEMOGRAPHICS, MEDICAL HISTORY AND TTP RECURRENCE INFORMATION

The statistical evaluation will be descriptive using standard statistical tools (including mean, standard deviation, median, maximum, and minimum) for continuous variables and counts and percentages for categorical variables.

3.6.4. EVALUATION OF EFFICACY PARAMETERS

The following efficacy analyses will be performed:

- TTP-related events (defined as TTP-related death, recurrence of TTP or reported major thromboembolic event [e.g., myocardial infarction, cerebrovascular accident, pulmonary embolism or deep venous thrombosis]):
 - Summary of the (cumulative) proportion of subjects with TTP-related events over time (including after 12M FU visit, after 24M FU visit, and after 36M FU visit), as well as the number of such events.
 - Summary of the time to first TTP-related event (starting from screening/baseline visit), based on a Kaplan-Meier (KM) analysis.
- Mortality: mortality rate during the study.
- Recurrence of disease:
 - Summary of the (cumulative) proportion of subjects with recurrence of disease over time (including after 12M FU visit, after 24M FU visit, and after 36M FU visit), as well as the number of such events.
 - Summary of time to first recurrence (starting from end of previous TTP episode), based on a KM analysis.
 - Summary of TTP recurrence information, including duration of daily PE.
 - Descriptive analysis of incidence of recurrence in relation to ADAMTS13 levels after previous TTP episode.
- Reported major thromboembolic events (e.g., myocardial infarction, cerebrovascular accident, pulmonary embolism or deep venous thrombosis):
 - Summary of the (cumulative) proportion of subjects with reported major thromboembolic events over time (including after 12M FU visit, after 24M FU visit, and after 36M FU visit), as well as the number of such events.
 - Summary of the time to first reported major thromboembolic event (starting from screening/baseline visit), based on a KM analysis.
- Cognitive assessment:
 - Summary of RBANS cognitive assessment score, including change from baseline, over time.
 - Descriptive comparison of RBANS cognitive assessment score with reference population.
- Quality of life assessment:
 - Summary of HIT-6 scores, including change from baseline, over time.
 - Summary of SF-36 scales, including change from baseline, over time, and at the end of recurrence period.

All efficacy endpoints related to assessments on the Q6M FU visits will be analyzed using the ITO population. Summarization will be conducted on the total study population and by analysis group. For the group-wise analysis, the following groups will be considered:

(1) caplacizumab-treated, defined as subjects in the ITO population who have been randomized to caplacizumab in Study ALX0681-C301, evaluated up to their first recurrence⁺⁺⁺; (2) standard of care-treated, defined as subjects in the ITO population who have been randomized to placebo in Study ALX0681-C301, evaluated up to their first recurrence.

All efficacy endpoints related to assessments during the recurrence period will be analyzed using the recurrence population. The effect of retreatment of caplacizumab on these endpoints will be evaluated.

Select sensitivity analyses may be planned to assess the effect of heterogeneity in the timings of the baseline visit between subjects. More details will be provided in the SAP. Unless specified otherwise, no missing data imputation will be applied, and all efficacy endpoints will be analyzed as observed.

3.6.5. EVALUATION OF PHARMACOKINETIC AND PHARMACODYNAMIC, DISEASE RELATED MARKERS AND IMMUNOGENICITY PARAMETERS

Individual study drug concentrations will be listed. In addition a listing of the actual sampling times relative to the study drug administration times will be presented.

Drug concentrations will be summarized by sampling time using descriptive statistics and will be listed and summarized in tabular and/or graphical form.

All PD and disease-related marker data will be summarized using descriptive statistics and will be listed and summarized in tabular and/or graphical form.

Immunogenicity will be assessed through listing of individual (ADA, mADA and nAb) results by subject, summary tables and immunogenicity time profiles. Immunogenicity data will be correlated with PK and PD readout using descriptive statistics per subject category based on pre-Ab and TE ADA status (using ADA results obtained in Study ALX0681-C301), summarized in tabular and/or graphical form. In addition, immunogenicity will be correlated with possible safety findings. The effect of retreatment with caplacizumab on immunogenicity will be assessed.

⁺⁺⁺ Subjects who had a recurrence during Study ALX0681-C301 or between the Final (28 day) FU visit in Study ALX0681-C301 and Screening/Baseline in Study ALX0681-C302, will not be considered for the group-wise analyses.

3.6.6. EVALUATION OF SAFETY PARAMETERS

The DSMB will evaluate the safety data periodically (see section [3.1](#)).

The following analyses will be performed to assess the safety of subjects in this study.

- The incidence and type of AEs.
- The incidence and type of SAEs.
- The incidence and type of related AEs (including bleeding-related AEs, PE-related AEs, and corticosteroid-related AEs).
- The laboratory parameters and change from baseline in these laboratory parameters.

All safety analyses will be performed using the ITO population for the overall study period and using the recurrence population for recurrence periods specifically. Details will be provided in the SAP.

AEs will be fully described and coded according to the Medical Dictionary for regulatory Activities (MedDRA). Frequency of subjects presenting AEs, AEs leading to discontinuation of study drug, adverse drug reactions, and SAEs will be tabulated by system organ class and preferred term. AEs of special interest will be analyzed separately.

For laboratory parameters, descriptive statistics (mean, median, standard deviation, minimum, and maximum) will be computed on the actual values and the change from baseline. All laboratory values will be categorized according to their normal ranges as below, within or above normal. A shift table versus baseline will be created.

Vital signs variables will be fully depicted using descriptive statistics.

Abnormal findings in physical examinations will be listed.

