A total of 574 TEAEs were reported in 34 (97.1%) subjects in the caplacizumab treatment group compared with 545 TEAEs in 37 (100%) subjects in the placebo treatment group. No subjects in the caplacizumab treatment group died during the study. Two subjects in the placebo treatment group died between the end of study treatment up to and including 1 month FU: one subject had a treatment emergent adverse event (TEAE) of cerebral hemorrhage which was assessed as related to TTP; the other died from the serious TEAE of refractory TTP. Serious adverse events (SAEs) were reported in a similar number of subjects in the two treatment arms (57.1% in the caplacizumab group and 51.4% in the placebo group). The number of subjects with any TEAE leading to discontinuation of study drug was 4 and 2 in the caplacizumab and placebo groups, respectively.

The occurrence of treatment-emergent major thromboembolic adverse events was investigated in the clinical study database, using the Standardized MedDRA Query for 'embolic and thrombotic events'. The proportion of subjects with at least one of these events together with the total number of events were summarized and reported per treatment group. Transient episodes were not considered major thromboembolic events and

were, therefore, not included in this analysis. TTP-related mortality during the study was evaluated based on AE reporting, with relatedness to TTP as judged by the Investigator. The safety population consisted of 35 caplacizumab-treated and 37 placebo-treated subjects. Four major thromboembolic events were reported in 4 subjects in the caplacizumab group (1 pulmonary embolism and 3 TTP exacerbations). In the placebo group, 20 major thromboembolic events were reported in 14 subjects (2 acute myocardial infarctions, 1 ischemic and 1 hemorrhagic stroke, 1 pulmonary embolism, 1 deep vein thrombosis, 1 venous thrombosis and 13 TTP exacerbations). Two TTP-related deaths occurred during the study, both in the placebo treatment group (causes of death: refractory TTP and cerebral hemorrhage). In total, 11.4% of caplacizumab-treated subjects versus 43.2% of placebo-treated subjects experienced one or more thromboembolic events or died. The results of this analysis suggest that treatment with caplacizumab has the potential to reduce the significant morbidity and mortality associated with acquired TTP.

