2.1.4 Safety endpoints

The safety analysis will be based on the reported adverse events and other safety information, such as clinical laboratory data, vital signs and physical examination.

Observation period

The observation period will be divided into 2 non mutually exclusive periods: the on-study period and the recurrence period.

The on-study observation period is defined as the time from informed consent until the end of the study (defined as last protocol planned visit).

The recurrence period is from the start of the recurrence episode, defined as recurrent thrombocytopenia requiring initiation of daily PE, until the last recurrence follow-up visit of that episode. In case of treatment with the IMP, the recurrence period is divided into 2 epochs:

- the **treatment epoch** is defined as the time from the first administration of the IMP to the last administration of the IMP.
- the **residual treatment** epoch is defined as the time from the last administration of the IMP to the last administration of the IMP + 30 days.

The treatment-emergent adverse event (TEAE) period will include both treatment and residual treatment epochs.

In case treatment with the IMP is not initiated during the recurrence episode, there is no subdivision of the recurrence period into the treatment epoch and the residual treatment epoch. The adverse event occurring during that period are not identified as treatment-emergent adverse events.

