2.4.5.1 Analyses of adverse events

Generalities

The primary focus of adverse event reporting will be on treatment-emergent adverse events. Pretreatment and posttreatment adverse events will be described separately.

If an adverse event date/time of onset (occurrence, worsening, or becoming serious) is incomplete, an imputation algorithm will be used to classify the adverse event as pretreatment,

treatment-emergent, or posttreatment. The algorithm for imputing date/time of onset will be conservative and will classify an adverse event as treatment emergent unless there is definitive information to determine it is pretreatment or posttreatment. Details on classification of adverse events with missing or partial onset dates are provided in [Section 2.5.3](#).

Adverse events (AEs) will be placed into analysis periods according to their start date (time). The AE will only be presented in the analysis period during which it started, ie, period start date (time) \leq AE start date (time) \leq period stop date (time). There will be no imputation of other missing date (time) fields, nor of the missing parts of other partially known date (time) fields. When needed (e.g., an incomplete date (time) leads to a double phase allocation), the following rules will be applied: adverse events will be allocated on all analysis levels (ie, for analysis periods and subperiods, see [Section 2.5.4](#)) according to their start date (time). In case the adverse event (AE) start date(time) is incomplete, the allocation will be done according to the available parts of the AE start date(time) and taking into account the AE end date(time) (ie, the AE start date(time) cannot be later than the AE end date(time)):

- When, due to missing date (part) an allocation needs to be made to an analysis period, the AE will be allocated to the treatment phase and not off-treatment phase (worst-case allocation).
- When an allocation needs to be made to a specific recurrence period, the AE will be allocated to the first recurrence period.
- When an allocation needs to be made within a recurrence period, the event will be allocated to the daily PE subperiod.

Tables on the recurrence population will include only adverse events that occurred during the recurrence period, treatment-emergent (for patients who received the IMP) and non-treatment emergent (for patients who did not received the IMP).

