When cross-tabulating AE PTs versus an AE attribute (e.g., severity), the worst-case is always applied within each analysis period. This means that when a participant has the same AE PT twice in the same analysis period, then the participant is reported only once: with the worst severity. If this happens in two different analysis periods, the participant is reported twice: once in each analysis period.

AE onset day and AE duration are defined as follows:

- AE onset day
 - AE start date – reference date + 1 day (when the AE start date is completely known)
 - Missing (when the AE start date is incomplete or unknown).
 - Two different onset days will be calculated: one with the reference date being the screening/baseline visit; and the other, for adverse events occurring during the recurrence period, with reference date being the recurrence visit.
- AE duration
 - AE stop date – AE start date + 1 day (when both dates are completely known)

- Trial termination date – AE start date + 1 day (when the AE start date is fully known but the AE is not resolved at the end of the trial): in this case the duration will be presented as “>x days” in the listing rather than “x days”
- Missing (when the AE start date is incomplete or unknown, or when the AE has resolved but with an incomplete or unknown end date).

These derived parameters will only be presented in the listings. Note that the start and stop times of the AE are not used.

AE incidence tables will present by SOC and PT, sorted by decreasing frequency of SOC and PTs within SOCs, the number (n) and percentage (%) of participants experiencing an adverse event. The denominator for computation of percentages is the population within each treatment group.

The following analysis periods will be considered for all TEAEs tables on the recurrence population:

- Treatment daily PE period
- Treatment post-daily PE period
- Overall treatment period
- Follow-up period
- Overall recurrence period

The following analysis periods will be considered for AE occurring in the recurrence periods for patients not treated with the IMP:

- Daily PE period
- Post Daily PE period
- Overall recurrence period

The following analysis period will be considered for the adverse events observed during the study for the ITO population:

- Overall study period

Analysis of all adverse events

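### Adverse events in the full cohort are tabulated only over the whole study, recurrences included, so no planned table shows adverse events outside recurrences

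*Protocol*

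**What the plan says.** - **Periods for ITO adverse events.** Protocol 3.6.6: "All safety analyses will be performed using the ITO population for the overall study period and using the recurrence population for recurrence periods specifically". It leaves details to the SAP. SAP 2.4.5.1 supplies them: "The following analysis period will be considered for the adverse events observed during the study for the ITO population". The list that follows has one entry, the overall study period.
- **What that period contains.** SAP 2.1.4: "The on-study observation period is defined as the time from informed consent until the end of the study". The same section says: "The observation period will be divided into 2 non mutually exclusive periods: the on-study period and the recurrence period". Table 3 (SAP 2.5.4) shows one undivided observation phase.
- **The other view.** SAP 2.4.5.1: "Tables on the recurrence population will include only adverse events that occurred during the recurrence period".
- **A general statement.** SAP 2.4.5.1 also says: "Pretreatment and posttreatment adverse events will be described separately".
- **Seriousness of a recurrence.** Protocol 3.5.2: "All exacerbations and relapses must be considered covered by the" medically important event criterion, so each one is reported as an SAE. Protocol 3.4.9.1 repeats this.
- **Columns.** SAP 2.4.5 splits ITO safety by whether the subject ever received caplacizumab in C301, in the double-blind or open-label part (*Caplacizumab total* and *Not treated*). Recurrence-population columns are set by treatment in C302.
- **Contrast.** SAP 2.4.4 stops the efficacy groups at the first C302 recurrence. Protocol 3.1.1 drops twice-yearly visits that fall in a recurrence because their assessments would be confounded.

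**The concern.** Long-term safety is part of the first objective (Protocol 2, SAP 1.2). A reader of the ITO tables will want to know what happens to these subjects when they are not in an acute episode. The planned tables add to the follow-up events whatever arises during hospital care, plasma exchange, steroids and open-label caplacizumab for a new episode.

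Two features make this more than a matter of presentation. First, a recurrence is by rule an SAE, so the SAE row of each ITO column contains every relapser. Second, the columns are fixed by C301 exposure and are not cut at recurrence. A *Not treated* subject who relapses and meets the treatment criteria receives caplacizumab in C302 (Protocol 3.3.1), and events on drug are then counted under *Not treated*. Bleeding is the obvious example: in the phase II TITAN study 54.3% of caplacizumab subjects and 37.8% of placebo subjects had a bleeding-related TEAE (Protocol 1.2.4).

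The columns may also differ in recurrence risk. *Caplacizumab total* includes subjects who reached open-label drug in C301, and the route to it was an exacerbation, or a relapse during treatment extension (Protocol 1.2.4).

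**Working it through.** The plan states no sample size, power or error rate for these tables, so there is no figure to reproduce. The structural point comes from reading the plan. The arithmetic only illustrates size.

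**Step 1: is there a table for time outside recurrences?** The ITO period runs from consent to end of study with recurrences left in. Recurrence-population tables hold only events within recurrences. None of the summaries in SAP 2.4.5.1 is limited to time outside recurrences or before the first one.

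**Step 2: does the pretreatment/posttreatment sentence supply one?** Those terms are tied to dosing with study drug. Subjects with no recurrence, or with an untreated one, have no such periods in C302, and no ITO period or listed table carries the sentence out.

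**Step 3: can it be recovered by subtraction?** Partly. An event is shown only in the period in which it started, so whole-study event totals are roughly recoverable. Subject counts do not subtract, and the two sets of tables use different columns.

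**Step 4: the SAE row.** Let r be the recurrence risk and q the risk of a non-recurrence SAE, taken as independent. Both are assumed, because the documents give neither for C302.

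- P(any SAE) = 1 − (1 − q)(1 − r)
- q = 20%, r = 10%: 1 − 0.80 × 0.90 = 28%
- q = 20%, r = 30%: 1 − 0.80 × 0.70 = 44%
- Gap = (1 − q)(r₂ − r₁) = 0.80 × 0.20 = 16 points, with identical safety outside recurrences. For q = 10% it is 18 points; for q = 40%, 12 points.

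The gap scales with the difference in r. TITAN's figures for exacerbation and/or relapse were 36.1% and 33.3% (Protocol 1.2.4). That 2.8-point difference would give only 0.80 × 2.8 = 2.2 points.

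**Step 5: the any-AE row.** If 90% of subjects have some other AE and r = 18% (the median in the systematic review cited in Protocol 1.1, range 3–84%): 1 − 0.10 × 0.82 = 92%, against 90% without recurrences. This row hardly moves.

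**Step 6: event counts.** TITAN gives "A total of 574 TEAEs were reported in 34 (97.1%) subjects in the caplacizumab treatment group"; the safety population was 35, so 574/35 = 16.4 TEAEs per subject over that study. This is not a per-episode figure, so what follows is rough. With b assumed background events per subject over 3 years and one recurrence per relapser, the share of events from recurrences is 16.4r/(16.4r + b).

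| r | b = 2 | b = 5 | b = 10 |
|---|---|---|---|
| 3% | 20% | 9% | 5% |
| 18% | 60% | 37% | 23% |
| 84% | 87% | 73% | 58% |

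**Step 7: does the person-month rate correct for this?** No. The SAP rate is 100 × participants with an event ÷ months observed. A treated recurrence lasts about 5.9 + 30 + 7 = 43 days, or 71 days with a full 28-day extension (5.9 is TITAN's mean number of initial PE days in the caplacizumab group). That is 3.9–6.5% of about 1,096 days. It adds little time to the denominator, while the relapser enters the SAE numerator.

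**The case against.** The strongest reply is that an overall on-study table is legitimate: relapse belongs to the third objective, the long-term impact of TTP, and the study is descriptive with no formal tests. That stands, and it is why the overall tables should stay.

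There is also partial protection:

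- Listings give onset day from both the baseline visit and the recurrence visit.
- The SMQ bleeding and thromboembolic rows exclude the TTP preferred term.
- The group-wise efficacy analysis, which includes major thromboembolic events, is cut at first recurrence.
- Laboratory data from the twice-yearly visits are not affected, since those visits are not held during a recurrence.

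All of this stands and confines the point to adverse event tables. It does not supply the missing summary. Listings are not a table, and removing one term leaves the other events of the episode, the investigator-flagged bleeding row and the SAE row as they were.

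A reader might infer that the ITO columns largely reflect who relapsed. The documents do not support that. They give neither a C302 recurrence rate nor a background AE rate, and Step 6 runs from 5% to 87% on assumed inputs. The SAP percentages and rates count participants, so event totals do not enter them. Nor are long-term signals diluted in general: each preferred term has the treatment group as its denominator, so only terms that also occur in acute episodes are affected.

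**Conclusion.** The gap is real: ITO adverse events have one period, it contains recurrences, and no planned table shows events outside them. SAE, bleeding and SOC/PT rows can substantially reflect relapse, and events on caplacizumab given in C302 can be counted under *Not treated*.

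The size is unknown. The 28% versus 44% illustration rests on an assumed 20% non-recurrence SAE risk, assumed recurrence risks of 10% and 30%, and independence; with similar recurrence in both columns the gap would be small. The any-AE row and the twice-yearly laboratory data are not a concern. This is a cheap improvement that serves the first objective. It does not invalidate the planned tables.

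**What to change.** In SAP 2.4.5.1 and Table 3 (SAP 2.5.4), add two exhaustive, mutually exclusive adverse event periods for the ITO population:

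- **(a) Recurrence or treatment-emergent time:** from the recurrence visit to the later of the recurrence follow-up visit and the last dose of study drug + 30 days. For an untreated recurrence it ends at the follow-up visit. Overlapping windows count once.
- **(b) All other on-study time.**

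The later-of rule is needed because the treatment-emergent window runs to 30 days after the last dose (SAP 2.1.4), while the follow-up visit of a treated recurrence is about 7 days after it. Ending (a) at the visit and also removing the 30-day window from (b) would leave events from about day 8 to day 30 in neither period.

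Report AEs, SAEs and bleeding events for each period with its own person-months. Use (b) to describe long-term safety outside recurrences, and keep the protocol-specified overall tables alongside.

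The cost is SAP wording before database lock, one period flag built from dates the SAP already uses, and one more set of descriptive tables. No new data are needed. Relapsers contribute less time to (b), so its results should be read with the person-months.
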